8. STUDY VISITS

8.1. Pre-screening

Recruitment will commence once the clinical site has received approval from the IRB, and staff have been delegated to perform recruitment activities. Patients may self-present by contacting the study team as per the IRB-approved recruitment materials to complete the pre-screening procedure, at which point they will be scheduled for a screening and baseline visit. Any

UPH-STD-05-01 Version: 0

Effective Date: 06/23/2023 Page **20** of **44**

recruitment materials used will be approved by applicable regulatory bodies prior to distribution and/or use.

8.2. Visit 1 - Screening and Baseline (Day 0)

The delegated study staff will explain the study objectives, the process, and the modalities of participation in the research. The study staff will answer any questions the patient may have. Patients will then be given ample time to review the Informed Consent Form (ICF) and, ask any questions before signing the appropriate section(s). The ICF will then be signed by the Investigator or delegate. A copy of the Informed Consent Form (ICF) will be provided to the patient for their records. The informed consent process will be documented in the source documents.

Once the ICF is signed by the patient and attested to by the Investigators or delegate, the study staff will collect demographic information, vital signs and relevant medical history, and conduct an examination in order to verify the eligibility criteria (excluding urine analysis results).

If the patients meet the inclusion criteria and none of the exclusion criteria (excluding urine analysis results), urine specimens will be collected using acceptable methods (refer to section 9.1). The collected urine specimens will be analyzed by both urine PCR and C&S in accordance with SOPs.

Prior to Visit 2 and upon confirmation of eligibility by an Investigator, patients will be enrolled into the study and will be randomized into one of two study arms (PCR-arm or C&S-arm).

8.3. Visit 2 - Treatment (Day 0 + 5)

Visit 2 MUST initiate within 24 hours of the test result (urine C&S or urine PCR as applicable to subject's assigned arm) becoming available and within specified buffer window. Study staff will record the data associated with the PCR test report or C&S test report in a dedicated eCRF, including time of the test reports.

Visit 2 may be conducted virtually, as per treating Investigator's discretion, if the patient care can be continued in an out-patient clinic/setting.

The identity of the patient will be confirmed by verbal verification of DOB and name. The Investigator or delegate will review medical history. Patients will be asked about any changes in their health, and any concomitant treatments administered since the last visit.

UPH-STD-05-01 Version: 0

Effective Date: 06/23/2023

Page 21 of 44

Doc Lab Inc. / Protocol Number 22-UPHUV-01 Advarra IRB Approved Version 0, Date: 12 May 2023 / Pro00071764

The treating Investigator will utilize the results of the patients' randomly assigned study arm for their clinical decision making and patient care. The treating Investigator MUST NOT* review the results of the (unassigned) comparator test before treatment.

*Exception: If the patient's assigned test detects no UTI, the treating Investigator will review the result of the comparator test. In the case of concordant result between two comparators (both negative), the patient will be referred to SOC and excluded from the study. In the case of discordant result, the patient will be referred to SOC and the result of patient care will be followed up by the Investigator or delegate. The patient data will be collected and used for discordant analysis as planned (refer to section 11.3.4).

The treating Investigator shall provide continuous patient care as per their medical decision(s). These include, but are not limited to: request of unscheduled visits, admission/referral of patient to receive in-patient care, administration of IV or oral antibiotics, in/out-patient care, or use of broad-spectrum antibiotics.

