2.2. Schedule of Assessments

The schedule of assessments table provides an overview of the protocol visits and procedures. The investigator may schedule visits (unscheduled visits) in addition to those listed on the schedule of assessments, in order to conduct evaluations or assessments required to protect the well-being of the subject.

Table 1. Schedule of Assessments

Assessments	Screening and Baseline V1 (Day 0)	Treatment ⁱ V2 (Day 0 to 5)	End-of-Study V3 (Day 28 ± 7)	Unscheduled Visit ⁱ UV
Informed Consent	X			
Eligibility Criteria	X	X		
Demographics ^a	X			
Medical history	X			
Vital signs ^b	X		X	X
Physical Examination	Х		X	X
Concomitant therapy	Х	X	X	X
Randomization	X			
Urine sample	Х		X	Х
collection				
Urine PCR	X		X	xe
Urine C&S	X		X	xe
cUTI treatment		$\mathbf{X}^{\mathbf{f}}$	X ^d	X
Adverse events ^c	X	X	X	X
Study conclusion			X	X

¹ Treatment visit (Visit 2) and/or unscheduled visits may be conducted virtually

UPH-STD-05-01 Version: 0

Effective Date: 06/23/2023 Page 12 of 44

^a Demographics include sex, age, date of birth

^b Vital signs include body temperature (°C), SBP (mmHg), DBP (mmHg), HR (bpm) and may be conducted by the Investigator at their discretion

^c AEs will be collected from the time of informed consent to EOS. Any ongoing AEs at EOS will be followed until resolution or stabilization

^d cUTI treatment may continue at EOS and after patient's study exit

^e Additional urine testing (PCR, C&S, or both) may be ordered at unscheduled visits at treating Investigator's discretion

^f cUTI treatment must initiate within 24 hours of receiving the test results (either PCR or C&S as per subject's assigned arm)

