7.5. Blinding and Unblinding

The treating Investigator will only have access to the results of their patients' assigned test, and will be blinded to the result of the comparator test until after the end of the study.

The treating Investigator shall gain an access to the result of comparator test in following cases:

- If a patient's assigned test result comes back negative UTI.
- If a patient is withdrawn from the study. In the opinion of the Investigator, it is not in the best interest of the patient to continue study therapy and/or lack of efficacy.
- If patient decide to discontinue study participation.

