11. STATISTICAL EVALUATION

11.1. Sample Size

The sample size calculation was conducted using the software package G*Power (v3.1.9.7) on a two-group independent proportions Fisher's exact-test (one-tailed), chosen as the statistical test for the primary endpoint of this study. A type I (α) error probability of 0.05, and a power (1 – β) of probability 0.85 was chosen for the calculation; an allocation ratio of 1:1 was set to address the equally-sized treatment arms.

According to literature, patient populations that used C&S testing for cUTI management has a favorable clinical outcomes (FCl)percentage ranging from 60%-90% 8. For the purpose of this study, we assumed an FCl percentage of 75% for the C&S arm. A 10% expected improvement of the FCl in the PCR arm will require 574 enrolled participants. Assuming a 25% attrition rate & post-hoc exclusion rate (due to PCR or C&S negative result after randomization), up to 146 additional participants will be enrolled. Thus, up to 720 participants will be sufficient for

UPH-STD-05-01 Version: 0

Effective Date: 06/23/2023 Page **27** of **44**

Doc Lab Inc. / Protocol Number 22-UPHUV-01

Advarra IRB Approved Version 0, Date: 12 May 2023 / Pro00071764

completion of the study. The participants will be enrolled in at least 6 study sites (with an equal distribution of participants enrolled per site).

Exact - Proportions: Inequality, two independent groups (Fisher's exact test)

Options: Exact distribution

Analysis: A priori: Compute required sample size Input: Tail(s) = One Proportion p1 = 0.7 Proportion p2 = 0.8 α err prob = 0.05 Power (1- β err prob) = 0.85

Allocation ratio N2/N1 = 1

Output: Sample size group 1 = 287

Sample size group 2 = 287 Total sample size = 574

Actual power = 0.8513193Actual α = 0.0404397

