11.2. Study Population

The Intention-to-Treat (ITT) population: All participants who participate in the study and get randomized into one of the study's arm, without any major protocol violations which would significantly compromise the integrity of collected data.

The Modified Intent-To-Treat (Mod-ITT) Population: All participants from the ITT with a positive PCR or C&S results after randomization assignment.

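### Patients with discordant baseline tests can be treated on the unassigned result, and Sections 8.3, 11.1 and 11.2 do not agree on whether they are in the primary analysis

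*Combined protocol and SAP*

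**What the plan says.** Both tests are run on every baseline urine sample (Sections 5.1 and 8.2). The treating investigator sees only the assigned result and "will be blinded to the result of the comparator test until after the end of the study" (Section 7.5). One of the three exceptions in Section 7.5 is a negative assigned test. Section 8.3 makes that exception an instruction: "If the patient's assigned test detects no UTI, the treating Investigator will review the result of the comparator test". It is attached to the rule against looking at the unassigned result before treatment, so the look comes before treatment.

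Section 8.3 then splits these patients. Those negative on both tests go to SOC and leave the study. Discordant patients go to SOC and are followed up, and the only use named for their data is the discordant analysis. The note to the schematic in Section 5.2 bases SOC treatment on the diagnostic evidence and the investigator's judgement. By then the evidence includes the other test.

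Two later sections bear on who is analysed:

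- Section 11.2 defines the Mod-ITT as "All participants from the ITT with a positive PCR or C&S results after randomization assignment", and Section 11.3.1 makes it the primary analysis set.
- Section 11.1 allows 25% for attrition together with a "post-hoc exclusion rate (due to PCR or C&S negative result after randomization").

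Footnote e of the schedule (Section 2.2) adds: "Additional urine testing (PCR, C&S, or both) may be ordered at unscheduled visits at treating Investigator's discretion".

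**The concern.** Discordant patients are the ones in whom the two tests would lead to different care, so they carry much of the information about PCR-guided versus culture-guided management. The plan lets them be treated with the unassigned result and then does not settle whether they count. Nothing says whether PCR or C&S means either test, both tests or the assigned test, and no sensitivity analysis covers the alternatives.

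The trial is open-label. If the question is settled after outcomes are known, the primary result depends on a choice made with the data in view. The choice also changes what is estimated and with what power.

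**Working it through.** **1. One patient through the text.** Take a C&S-arm patient, culture-negative and PCR-positive.

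| Section | Consequence for this patient |
|---|---|
| 7.5, 8.3 | PCR result opened before treatment |
| 5.2 note, 8.3 | SOC, which can use the PCR result |
| 8.3 | Followed up; data named only for the discordant analysis |
| 11.2, 11.3.1 | Positive on one test: in the primary set |
| 11.1 | Negative on one test: counted as a post-hoc exclusion |

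A PCR-arm patient who is PCR-negative and culture-positive follows the mirror-image path. The C&S arm is probably affected more, because Section 3 expects PCR to be more sensitive.

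**2. The plan's own figure.** Section 11.1 specifies a "two-group independent proportions Fisher's exact-test (one-tailed"), "A type I (α) error probability of 0.05", and power "of probability 0.85 was chosen for the calculation". Its software output uses 0.70 and 0.80. Exact enumeration gives power 0.8513 at 287 per arm and 0.84997 at 286, so 574 reproduces. With equal rates of 0.70 the test rejects 4.1% of the time.

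**3. Reading A: positive on either test, discordant patients kept.** Both tests are run on everyone, so membership does not depend on arm and the arms stay comparable. The cost is dilution. Assume a share f of the C&S arm is culture-negative and PCR-positive and gains a fraction b of the 10-point benefit, with no crossover in the PCR arm:

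C&S rate = 0.70 + 0.10 × b × f, PCR rate = 0.80, 287 per arm.

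| f | C&S rate, b = 1 | Power | C&S rate, b = 0.5 | Power |
|---|---|---|---|---|
| 0 | 0.700 | 0.85 | 0.700 | 0.85 |
| 10% | 0.710 | 0.78 | 0.705 | 0.82 |
| 20% | 0.720 | 0.70 | 0.710 | 0.78 |
| 30% | 0.730 | 0.60 | 0.715 | 0.74 |

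The text of Section 11.1 states 75% for the C&S arm, not 70%. At 0.75 versus 0.85 with b = 1, power goes from 0.90 to 0.84, 0.76 and 0.66.

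**4. Reading B: anyone negative on either test is dropped.** This is the literal sense of the Section 11.1 parenthesis. Only patients positive on both tests remain. The arms are alike and the Section 8.3 exception cannot be triggered by the baseline tests, but every patient in whom the tests differ is lost.

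**5. Reading C: negatives on the assigned test are dropped.** The PCR arm keeps PCR-only positives and the C&S arm discards them, so the arms hold unlike patients. Assume no true effect, 360 randomized per arm, 50% positive on both tests, 5% culture-only, a share u PCR-only, and 70% success in culture-positives:

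- C&S arm: n = 360 × 0.55 = 198, rate 0.70.
- PCR arm: n = 360 × (0.50 + u), rate = (0.50 × 0.70 + u × s) / (0.50 + u), where s is success in PCR-only positives.

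| u | s | PCR-arm n | PCR-arm rate | One-sided rejection |
|---|---|---|---|---|
| 30% | 55% | 288 | 0.644 | 0.1% |
| 15% | 65% | 234 | 0.688 | 2.3% |
| any of 15–30% | 70% | 234–288 | 0.700 | about 4% |
| 15% | 75% | 234 | 0.712 | 7% |
| 25% | 85% | 270 | 0.750 | 29% |
| 30% | 85% | 288 | 0.756 | 36% |

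The error rate can move either way, because the documents do not say whether PCR-only patients do better or worse.

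**The case against.** The strongest reply is that the operative rules already agree. Section 11.2 defines the analysis set, Section 11.3.1 assigns it to the primary endpoint, and Section 8.3 removes from the study only patients negative on both tests. Section 8.3 says that discordant data go to the discordant analysis, but not that they go nowhere else. The Section 11.1 wording explains an enrolment allowance and does not define a population. On this view discordant patients stay in, and comparing strategies with fallback is legitimate in an open-label utility study. This is the most natural joint reading, and it lowers the severity. It does not remove the conflict with Section 11.1, and no text states the fallback estimand.

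The dilution figures can also be challenged. A crossed-over C&S patient has already waited for culture, which Section 3 puts at 48 hours or more, so any gain from speed is lost; hence the half-benefit column. The planned 70% and 80% might already include fallback, in which case there is no further dilution. Both points stand, and the figures are illustrations only.

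A reader might infer more than the documents support:

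- **That the plan must either contaminate the C&S arm or compare unlike patients.** Reading B does neither, and under Reading A the crossover rule applies to both arms.
- **That the false-positive rate is inflated.** That needs Reading C, which no section states, and PCR-only patients who do better, which nothing supports.
- **That footnote e contradicts Section 7.5.** The footnote concerns new testing at unscheduled visits, while Section 7.5 concerns access to the comparator result. It is a possible further route to the unassigned method, of unknown size.

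**Conclusion.** The point holds as an unresolved definition of the primary population for discordant patients, together with an unstated estimand. It should be fixed, but it is not a fatal flaw: the literal Mod-ITT definition already gives comparable arms, and double-negatives are out under every reading.

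Under that definition the issue is dilution and a changed question, not selection bias. Power is 0.60 to 0.78 with full benefit, or 0.74 to 0.82 with half, for 10% to 30% of the C&S arm affected, against 0.85 planned. These figures rest on assumed shares, no crossover in the PCR arm, and planned rates that exclude fallback. The range of about 0.1% to 36% for the one-sided error belongs only to the assigned-test reading and its assumed inputs. It shows why that reading should be closed off and does not forecast the trial's error rate.

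**What to change.** 1. In Sections 8.3, 11.1 and 11.2, state that every randomized patient positive on either baseline test is analysed for the primary endpoint in the assigned arm, and that only double-negatives leave the Mod-ITT on account of test results. Correct the Section 11.1 parenthesis to match.
2. Pre-specify a supportive analysis of the primary endpoint in patients positive on both baseline tests. Its drawback is size: on the assumed split in step 5 of the working it would hold 360 × 0.50 = 180 per arm before losses, against 360 × 0.70 = 252 to 360 × 0.85 = 306 in the either-positive set.
3. State that the primary result compares test strategies including fallback to the other test, and report by arm how many patients had the unassigned result opened. A negative assigned result with an eligible discordant comparator already identifies most of them; one eCRF field would capture the rest.
4. As a secondary matter, reconcile footnote e of the schedule with the access cases in Section 7.5.

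The cost is wording in a few sections, one supportive table and at most one eCRF field. Patient care is unchanged and no patients are added. The change does not restore power lost to dilution. It fixes the primary population in advance and shows how far fallback weakens the contrast.

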8.4. Visit 3 - End-of-Study (Day 28 ± 7)

EOS assessment should be performed in-person within the specified buffer period. The Investigator or delegate will perform/collect the following:

- Vital signs
- Physical examination (may be complete, targeted, or omitted; discretion of the Investigator)
- Record(s) of any adjunctive therapeutic procedures performed
- Record(s) of concomitant medications
- Assessment of clinical outcome(s)
- Record(s) of any AEs/SAEs

Urine specimens will be collected for microbiological evaluation. In case the result of urine specimen identifies an unsuccessful treatment, the patient may be followed-up to verify the final clinical outcome if deemed necessary by the treating Investigator.

When both the results of urine C&S and urine PCR become available, the treating Investigator will answer an evaluation questionnaire concerning his/her judgement of the diagnostic test and therapeutic value of urine PCR and urine C&S.

In case of clinical failure* as determined by treating Investigator at EOS, the patient's condition will be considered an AE and followed-up accordingly.

*Clinical failure is defined as a patient who has 1) on-going AE/SAE at EOS and/or 2) persistent cUTI symptoms and/or 3) developed new symptoms of cUTI.

UPH-STD-05-01 Version: 0

Effective Date: 06/23/2023 Page **22** of **44**

At the end of the study, the Investigator will complete the Study Exit Form present at the end of the eCRF portfolio. This form must also be completed in the event of premature termination of the patient's participation should they, the Investigator, or the Sponsor choose to discontinue their participation.

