6. SUBJECT SELECTION AND WITHDRAWAL

6.1. Inclusion Criteria

Subjects must meet all of the following criteria to be considered eligible for admission to the study:

- I1. At least 18 years of age at the time of consent;
- I2. Presenting at least two of the following new, persistent or worsening cUTI signs and symptoms at screening visit:
 - a) fever (temperature >38 degrees Celsius or >100.4 degrees Fahrenheit), hypothermia (temperature <35.5 degrees Celsius or <95.9 degrees Fahrenheit), rigors, or chills
 - b) dysuria, urinary frequency, urgency, or hematuria
 - c) suprapubic pain or pelvic pain
 - d) costovertebral angle (CVA) tenderness
 - e) nausea or vomiting
 - f) radiographic evidence of pyelonephritis
 - g) leukocytosis
- I3. Urine specimen with evidence of pyuria
 - a) dipstick analysis positive for nitrite and/or leukocyte esterase, or;
 - b) \geq 10 white blood cells (WBCs) per cubic millimeter [mm3], or;
 - c) \geq 10 WBCs per high power field (hpf), or;
 - d) clinically suspected pyuria (e.g. change in urine color, sediment in urine, or foul-smelling urine)

UPH-STD-05-01 Version: 0

Effective Date: 06/23/2023 Page 17 of 44

Doc Lab Inc. / Protocol Number 22-UPHUV-01 Advarra IRB Approved Version 0, Date: 12 May 2023 / Pro00071764

- I4. Having cUTI that requires microbiological diagnosis and treatment as suspected by the Investigator;
- I5. Presenting active UTI that failed to resolve on first-line therapy or identified as a high-risk* patient population;
 - *High-risk patient population include those who are elderly (≥65years), male, pregnant, having recurrent UTI (≥3/year), with underlying co-morbidities (e.g. diabetes, immunosuppression, or CKD), or with known functional and anatomical abnormalities of the urinary tract (e.g. stones, stents, recent instrumentation, indwelling catheters, neurogenic bladder, or PKD)
- I6. Able to provide at least 8 mL urine at visit 1 and 3;
- I7. Willing to abstain from sexual intercourse or use condoms during any sexual contact until the EOS visit is complete;
- I8. Willing to comply with protocol requirements, including availability for follow-up for the duration of the study.

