9.4. Physical Examination

The Investigator or delegate will perform a physical examination at V1 and V3. The physical examination may be complete, targeted, or omitted at the Investigator's discretion, based on the patient's condition and circumstances.

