11.3.2. Primary and Secondary Endpoints

The primary endpoint is the number (and percentage) of patients in each study arm with FCl at the EOS visit; this term is defined as a *clinical response of improvement* and/or *clinical cure*:

Clinical response of improvement is defined as:

1) Resolution of cUTI signs and symptoms present at baseline, and/or

UPH-STD-05-01 Version: 0

Effective Date: 06/23/2023 Page **28** of **44**

- 2) Development of no new cUTI symptoms, and/or
- 3) Avoidance of parenteral antibiotic therapy, in or out of hospital, at any time after randomization

Clinical cure is the resolution of all acute signs and symptoms of cUTI and improvement to such an extent that no further antimicrobial therapy (IV or oral) is required for the treatment of the cUTI

The secondary endpoints include:

- Number (and percentage) of patients in each arm with *microbiological eradication* of all baseline pathogens at the EOS visit; *microbiological eradication* of all baseline pathogens is defined as an end of study quantitative urine culture shows all uropathogens found at baseline are reduced to <10⁵ CFU/mL and all baseline pathogens are not detected by EOS urine PCR (Cq>33)
- Subjective measurement of Treating Investigator Satisfaction Score as evaluated by the questionnaire at EOS
- Turnaround Time (TAT: as measured in hours) of molecular diagnostic procedures compared to conventional diagnostics (time from collection of samples to complete identification of organism(s) and availability of antibiotic sensitivity results)
- Overall agreeability between the diagnostic results generated by PCR versus C&S as assessed by discordant analysis

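### The primary endpoint is judged partly on resolution of baseline signs, but the end-of-study examination may be omitted and no rule says how an unchecked sign is scored

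*Combined protocol and SAP*

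**What the plan says.** **Entry.** Section 6.1, criterion I2, needs any two of seven items. Items a to e are fever, hypothermia, rigors or chills; urinary symptoms; suprapubic or pelvic pain; CVA tenderness; and nausea or vomiting. Item f is "f) radiographic evidence of pyelonephritis" and item g is leukocytosis.

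**Endpoint.** In section 11.3.2 a favorable outcome is improvement and/or cure. The first element of improvement is "Resolution of cUTI signs and symptoms present at baseline". The other two are no new symptoms and avoidance of parenteral antibiotics. Cure is stricter: "Clinical cure is the resolution of all acute signs and symptoms of cUTI and improvement to such an extent" that no further antimicrobial therapy is needed.

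**Assessment at Visit 3.** Section 8.4 lists vital signs, an assessment of clinical outcome, and "Physical examination (may be complete, targeted, or omitted; discretion of the Investigator". Section 9.4 repeats the permission: "The physical examination may be complete, targeted, or omitted". Table 1 marks vital signs and examination at Visit 3, but its footnote b says vital signs "may be conducted by the Investigator at their discretion". Sections 9.2 and 9.3 say without qualification that temperature, blood pressure and heart rate will be measured at Visits 1 and 3. Table 1 has no row for a blood count or imaging at any visit. Section 4 mentions only unspecified relevant laboratory tests, for safety.

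**Failure and forms.** Section 8.4 defines clinical failure by ongoing adverse events, persistent symptoms or new symptoms; persistent signs are not named. The Appendix I questionnaire counts significant improvement as clinical improvement and offers an indeterminate category.

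**The concern.** Most urinary symptoms can be established by asking. CVA tenderness, a radiographic finding and a raised white-cell count cannot. A patient who entered on dysuria plus CVA tenderness can complete Visit 3 fully within protocol, with the dysuria gone and the tenderness never re-examined, and be recorded favorable. For radiographic pyelonephritis or leukocytosis the schedule never produces the observation that would show resolution.

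The trial is open-label. Section 7.5 withholds the unassigned test's result from the treating investigator, but not the arm. The same person treats, decides whether to examine, and judges the outcome. If signs are missed equally often in both arms, the difference shrinks and power is lost. If the decision to look differs by arm, the primary comparison is biased. An examination that was not done cannot be recovered after data collection.

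**Working it through.** **Step 1. Can each I2 item be reassessed at Visit 3 as the plan stands?**

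| I2 item | What is needed | Visit 3 provision |
|---|---|---|
| a, fever or hypothermia | Temperature | Required by 9.2 and listed in 8.4; footnote b conflicts |
| a (rigors, chills), b, c, e | Mostly a question to the patient | In-person visit with outcome assessment; no item-level record specified |
| d, CVA tenderness | Examination | May be omitted (8.4, 9.4) |
| f, radiographic pyelonephritis | Imaging | Not scheduled |
| g, leukocytosis | Blood count | Not scheduled |

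The gap lies mainly in d, f and g, and in fever only if footnote b is followed.

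**Step 2. Does a favorable outcome depend on resolution?** Section 11.3.2 ends the first improvement element with a connector, "Resolution of cUTI signs and symptoms present at baseline, and/or", and the second likewise, "Development of no new cUTI symptoms, and/or". Read literally, any one element suffices, so a patient with a persisting sign can be favorable. In the synopsis and Table 2 the connector stands only before the third element, which leaves it unclear whether the first two are both needed. Cure does require resolution of all acute signs. The unchecked sign therefore matters for cure and for the first improvement element. It decides classification only where resolution is treated as necessary.

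**Step 3. Reproduce the plan's power.** Inputs from section 11.1: one-tailed Fisher exact test, alpha 0.05, 287 per arm, rates 0.70 and 0.80. Power is the sum, over all pairs of success counts at which the Fisher p-value is at most 0.05, of the product of the two binomial probabilities. Result: 0.8513, matching the stated 0.8513193. With 0.80 in both arms the rejection rate is 0.0404, matching the stated actual alpha.

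**Step 4. Equal misclassification in both arms.** Let f be the share of true failures scored favorable because a persisting sign was not checked. The observed rate is p + f(1 − p). At f = 10%: 0.70 + 0.10 × 0.30 = 0.73, and 0.80 + 0.10 × 0.20 = 0.82. The observed difference is 0.10 × (1 − f).

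| f (assumed) | C&S | PCR | Power |
|---|---|---|---|
| 0 | 0.700 | 0.800 | 0.851 |
| 1% | 0.703 | 0.802 | 0.847 |
| 5% | 0.715 | 0.810 | 0.829 |
| 10% | 0.730 | 0.820 | 0.803 |
| 20% | 0.760 | 0.840 | 0.745 |
| 30% | 0.790 | 0.860 | 0.678 |

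**Step 5. Misclassification in the PCR arm only, no true effect.** Both true rates are 0.70, and the observed PCR rate is 0.70 + f × 0.30.

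| f (assumed) | Lift in points | One-sided false-positive rate |
|---|---|---|
| 0 | 0 | 0.041 |
| 1% | 0.3 | 0.049 |
| 2% | 0.6 | 0.057 |
| 5% | 1.5 | 0.090 |
| 10% | 3 | 0.174 |

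A lift in the C&S arm would work the other way, against the PCR arm. Nothing in the documents indicates a direction.

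**The case against.** Several stronger readings are tempting, and the documents do not support them.

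- **That the endpoint requires every baseline sign to have resolved, so the responder rule cannot be applied.** Under the literal connectors in section 11.3.2 the rule can classify these patients without the sign. Only cure plainly requires resolution. This objection stands, and it means that repairing the examination alone would not be enough.
- **That an unchecked sign is scored as resolved by default.** No default is written anywhere. Appendix I has an indeterminate category with a reason field. However, nothing sends an unassessed sign there, and section 11.3 does not say how that category enters the Fisher test.
- **That temperature may simply be skipped at Visit 3.** Sections 8.4 and 9.2 say otherwise. Footnote b is an inconsistency to reconcile, not a settled permission.
- **That the lack of a sign checklist in Table 1 shows none will exist.** Section 16.3 has the case report forms built after protocol finalization, and section 8.4 does list an outcome assessment.
- **That the power loss is large.** Only failures whose sole remaining evidence is an unexamined sign are affected; a patient with persisting dysuria or pain can be asked. At 1% to 5% the loss is small (0.847 to 0.829). The text of section 11.1 assumes 75% for C&S, unlike its software output. At 75% versus 85%, power starts at 0.898 and is still 0.859 at f = 10%.

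What survives is the written permission to omit an assessment that feeds the primary endpoint, together with the absence of any scoring rule for what was not assessed.

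**Conclusion.** The concern holds as a narrow gap in how the primary endpoint is ascertained, mainly for patients with CVA tenderness, radiographic pyelonephritis or leukocytosis at baseline. The plan judges the outcome partly on resolution of signs. It lets an investigator who knows the arm omit the examination, schedules neither of the other two measurements, and gives no rule for an unchecked sign.

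The size is unknown, because the documents give neither the share of patients entering on these signs nor a misclassification rate. The tables show a range from negligible to serious. One-arm misclassification is the more damaging case, but it assumes that examination practice differs by arm, which is possible in an open-label design and not shown. The point is worth correcting because the correction is cheap and has to precede data collection. It is secondary to the ambiguous endpoint definition and should be repaired together with it.

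**What to change.** 1. In sections 8.4 and 9.4, remove the option to omit the Visit 3 examination for items that feed the primary endpoint. Reconcile Table 1 footnote b with sections 8.4, 9.2 and 9.3.
2. At Visit 3, reassess each I2 item a to e that was positive at Visit 1 and record it as present, absent or not assessed. An item not assessed may not be entered as resolved.
3. In section 11.3.2, limit resolution scoring to items a to e, because f and g are not scheduled. A patient whose only I2 items are f and g has nothing to resolve under this rule and would otherwise meet it vacuously. State that such a patient is classified on the remaining criteria (no new symptoms, no further antimicrobial therapy) and is not counted as resolved by default.
4. State that a patient with an unassessed baseline item counts as not favorable in the primary Fisher test, with a sensitivity analysis that treats the outcome as missing.
5. Reconcile the connectors in the synopsis, Table 2 and section 11.3.2 with the failure definition in section 8.4 and the categories in Appendix I, so that resolution is a necessary element of a favorable outcome, apart from the patients in item 3. Otherwise a recorded persisting sign still leaves the patient favorable under section 11.3.2.

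**Cost.** Protocol wording and a short Visit 1 and Visit 3 checklist on the case report form. Visit 3 is already in person, with vital signs and examination listed. A targeted examination becomes compulsory for patients who had the sign at Visit 1, a few more outcomes will be scored not favorable, and the endpoint no longer claims resolution of radiographic findings or leukocytosis.
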